#### 3.2. Data conversion

In cases where the eCRF allows entering data in different units, respective data will be converted and the converted form will be used for analysis and for reporting.

- HbA1c will be converted to “%”
- BG values will be converted to mg/dL
- Length will be converted to “cm”
- Weight will be converted to “kg”

#### 3.3. Schedule of Assessments relevant for Analysis

| Procedure \ Visits                               | Visit 1
Screening | Visit 2
Baseline            | Visit 3        | Visit 4        | Visit 5        | Phone
Follow
up  |
|--|----------------------|--------------------------------|----------------|----------------|----------------|------------------------------------|
| Time point                                       |                      | day 1                          | week 13        | week 26        | week 39        |                                    |
| Time window
(+/- days)                        |                      | 0 to +14
days to
Visit 1 | ±14 days       | ±14 days       | ±14
days    | 2-5 days
>Visit 5               |
| Informed consent                                 | X        |                                |                |                |                |                                    |
| Eligibility check (inclusion/exclusion criteria) | X                    |                                |                |                |                |                                    |
| Pregnancy test (β-HCG urine)         | X                    | X                  | X  | X  | X  |                                    |
| HbA 1c in central lab                 | X        | X                              | X              | X              | X              |                                    |

| Procedure  | Visits            |                  |                |                 |                |                | Phone Follow up  |
|--|-------------------|------------------|----------------|-----------------|----------------|----------------|------------------------------|
|  | Visit 1 Screening | Visit 2 Baseline | Visit 3        | Visit 4         | Visit 5        |                |                              |
| Demographic data and other Baseline data         | X     |                  |                |                 |                |                |                              |
| Diabetes & diabetes treatment history            | X                 | X    |                |                 |                |                |                              |
| Diabetes medication                              | X                 | X    | X  | X   | X  |                |                              |
| Diabetes-associated diseases and treatment       | X                 | X    | X  | X   | X  |                |                              |
| Other diseases and medications                   | X                 | X    | X  | X   | X  |                |                              |
| Hypoglycemic events (severe, mild)               |                   | X                | X              | X               | X              |                |                              |
| Time of absence from work or school              |                   | X                | X              | X               | X              |                |                              |
| Height & weight                                  |                   | X                | X  | X   | X  |                |                              |
| Skin reactions                                   |                   | X                | X              | X               | X              |                |                              |
| Subject questionnaires                           | X                 |                  | X              | X               | X              |                |                              |
| Randomization                                    | X                 |                  |                |                 |                |                |                              |
| Distribution of devices and other study material |                   | X                | X              | X               |                |                |                              |
| Pump training                                    |                   | X    |                | X  |                |                |                              |
| Carbohydrate Counting Training                   |                   | X                |                |                 |                |                |                              |
| Device data download                             |                   |                  | X              | X               | X              |                |                              |
| A(D)Es/SA(D)Es                                   |                   | X                | X              | X               | X              | X  |                              |
| Malfunctions                                     |                   |                  | X              | X               | X              |                |                              |
| Collect study devices and other study material   |                   |                  |                | X               | X              |                |                              |

- 1 If ongoing A(D)E/SA(D)E at visit 5  
2 Written informed consent must be obtained prior to any study related procedure  
3 If applicable  
4 Performed in local lab  
5 Year of birth, gender, race; handedness, highest level of education, employment status, family status  
6 If any changes  
7 Weight only  
8 For group A and C  
9 if applicable by local law (e.g., in Austria)  
10 For group B and C

### 3.4. Handling of Withdrawals and other Missing Data

#### 3.4.1. Handling of missing data affecting the primary endpoint

As described in section 2.10, all randomized subjects will be part of the FAS group and thus be utilized for primary analysis. The status part (“Is this a problem now?”) of the DTQ will be completed by the subject before randomization. Thus it is ensured that status data is available for all subjects and that no bias is introduced by a potential preference of subjects for a particular group, which may result in a withdrawal of individual subjects right after randomization.

For subjects that answered the DTQ during Visit 4, these answers will be used for the primary analysis.

The following steps will be performed to handle missing change data:

In case of withdrawal, subjects will be asked to answer the DTQ questionnaire during the End of Study visit.

If it will not be possible to get questionnaire results at the End of Study visit but questionnaire results are available for week 13 (visit 3), these results will be used, i.e., a LOCF procedure will be applied.

If there are no results for week 13, e.g., because a subject withdrew before week 13, a value of 3 (“Same”) will be imputed as the answer to every individual question. This will result in a total score of 90, which corresponds to the expected mean result for the MDI group and thus represents a conservative imputation (the anticipated mean score for the Accu-Chek® Solo group is 110).

Technically, data acquired during the End of Study visit will be part of the Visit 5 eCRF variables. Consequently, the LOCF procedures described above will copy data from there. Should the End of Study data be not available, the respective data of the available last visit will be used.

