#### Subject Questionnaires

Subjects will be asked to complete a set of questionnaires at each visit, see section 7.10. These questionnaires will be presented electronically.

Upon completion of the questionnaires, the subject will press "Save" and close the document. This enables entries to be saved (in the eCRF). This will generate a notification to (named) study staff that the questionnaires have been completed/saved.

For the sake of confidentiality, neither the Investigator nor other study staff will be able to read the subject's entries.

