#### 3.4.2. Incomplete DTQ questionnaires

The handling of questionnaires that are missing completely is described in the previous section. It is however also possible, that questionnaires are only partially completed. Incomplete DTQ questionnaires will be handled according to the questionnaire’s “Scoring Instructions”. As

described above, a score between 1 and 5 is assigned to each possible answer, resulting in a maximum score of 150 if all answers are provided. If at least 22 questions have been answered, the sum score will be divided by the number of answered questions and multiplied by 30 to get a total sum. If 21 or less questions have been answered, the questionnaire will be treated as missing and handled according to the previous section.

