### **3.4.4. Handling of other missing data**

Missing values for scores other than the primary endpoint and those described in the previous section will be imputed using a LOCF approach, where applicable. In case of missing device data, where a LOCF approach would be meaningless, e.g., BG values or applied Insulin bolus and basal amounts, statistics will be calculated based on available information.

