### 3.5.3. Incomplete Dates

For a limited number of fields, the eCRF allows to enter incomplete dates in cases if the exact date is not known to the subject or the investigator, e.g., the date when diabetes was first diagnosed. For analysis, dates where only the year is known/given, July 1 will be used. If the month but not the day is known, 15 will be inserted as day. E.g., “2005” will be replaced by “01-Jul-2005” and “Sep-2010” will be replaced by “15-Sep-2010.

### 3.5.4. Special Handling of Visit 4

#### 3.5.4.1. Safety Events at Visit 4

Subjects randomized to treatment arm B (MDI) and C (OmniPod) will receive the Accu-Chek® Solo micropump system only at Visit 4. As a consequence, safety events (AEs and SAEs) cannot be assigned to either the randomized treatment or the Accu-Chek® Solo micropump system based on the date of the event alone. If an assignment to a device will be available from the investigator and confirmed by Safety, it will be used for the analysis. Otherwise, the event will be assigned to the Accu-Chek® Solo micropump system to guarantee conservative results.

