## **6.13. Special Analytical Issues**

### **6.13.1. Treatment of incomplete or unmonitored data due to Covid-19 pandemic risk mitigation**

The Covid-19 pandemic during the final phase of this study may impact data collection in two different ways. Firstly, in order to avoid the risk of infection at the study sites, some of the subjects did not come to the site in person for the final study visit (V5); this visit was then

performed as a phone-call visit (virtual visit). And secondly, monitoring of some subject data was not possible due to unavailability of site staff.

Neither of these restrictions or changes has any impact on the primary study results, i.e., on analysis of the DTQ.

However the following data from V5 are expected to be missing for those subjects that completed V5 virtually: weight, HbA1c, pregnancy test, skin reaction assessment, device data upload, return of study material.

Missing data will be handled according to the description in section 3.4; no specific analysis pertaining to virtual visits will be performed.

The lack of monitoring however may result in wrong or missing entries in the eCRF. The monitoring status of all variables used for analyses will therefore be extracted from the eCRF and all variables, that have not been monitored, will be displayed underlined in all listings.

Additionally, all descriptive statistics and statistical tests based on data, that include data not monitored will be performed twice. Firstly, using the data as entered in the eCRF and secondly based on data generated by removing the data, that has not been monitored, and replacing it according to the missing value treatment described in section 3.4.

Differences in the statistics obtained using these two different approaches will illustrate the potential impact the data not monitored may have on study results.

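### SAP 3.4 sets no barrier to imputation at the Visit 4 device switch, so MDI or OmniPod values can enter Visit 5 results and, rarely, a Solo rating can become a week-26 score

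*SAP*

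**What the plan says.** **The switch.** SAP 2.3 puts all subjects on Solo from Visit 4 to Visit 5. SAP 3.5.4.1 says that arms B and C "will receive the Accu-Chek® Solo micropump system only at Visit 4". SAP 3.5.4 then deals with the switch for safety events and device use time only.

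**Primary endpoint.** SAP 3.4.1 uses the Visit 4 DTQ if it was answered. Otherwise the order is the End of Study DTQ (in a step conditioned on withdrawal), then Visit 3, then 3 for every item, which totals 90. End of Study data "will be part of the Visit 5 eCRF variables. Consequently, the LOCF procedures described above will copy data from there". SAP 3.4.2 adds: "If 21 or less questions have been answered, the questionnaire will be treated as missing and handled according to the previous section".

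**Other data.** SAP 3.4.4 applies LOCF to other scores where applicable, and names one exception: "In case of missing device data, where a LOCF approach would be meaningless". SAP 6.13.1 expects HbA1c, among other items, to be missing when Visit 5 was done by telephone, and states: "Missing data will be handled according to the description in section 3.4; no specific analysis pertaining to virtual visits will be performed". It also repeats analyses that contain unmonitored data after "removing the data, that has not been monitored, and replacing it according to the missing value treatment described in section 3.4", and reads the result thus: "Differences in the statistics obtained using these two different approaches will illustrate the potential impact the data not monitored may have on study results".

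**Visit 5 results.** Protocol 6.3 has subjects who withdraw after Visit 2 perform Visit 5 as the early termination visit. SAP 6.2.1 summarises Visit 5 by arm and overall. SAP 6.8 to 6.8.1.1 compare Visit 4 with Visit 5 within arm. Protocol 11.6 names the week 26 to 39 DTQ change in groups B and C as an analysis.

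**The concern.** In arms B and C, Visit 5 results are meant to describe Solo use, and the Visit 4 to Visit 5 change is meant to describe what happens after moving to Solo. A value carried over the switch, or a record collected before it, says nothing about either. It pulls the change toward 0 and puts non-Solo values into Visit 5 tables. It also makes the check on unmonitored data hard to interpret, because the two runs can differ even when every entry is correct.

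The opposite direction touches the primary endpoint. A Solo rating used as the week-26 score of an MDI or OmniPod subject mixes treatments in the primary contrasts. Under the planning means it dilutes Solo versus MDI. For Solo versus OmniPod the direction is unknown, because the plan assumes no difference there.

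**Working it through.** **1. The plan's own figures.** Inputs (SAP 2.8): means 90 and 110, SD 30, two-sided alpha 0.05, 90% power, maximum drop-out 18%. A two-sample t-test needs 48.26, so 49 per group, with power 90.4% at 49. Then 49/0.82 = 59.8, so 60 per arm. Both figures reproduce.

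**2. Visit 5 routes, arms B and C.**

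- *Missing HbA1c.* SAP 6.13.1 refers it to 3.4. If LOCF is applied, the last earlier value is normally from Visit 4, on MDI or OmniPod. It is tabulated as Visit 5, and the Visit 4 to Visit 5 change is 0. The shift in the arm's Visit 5 mean is the share filled times the true change. Both inputs are assumptions: 10% × 0.1 = 0.01 points at the low end, 30% × 0.5 = 0.15 at the high end.
- *Unmonitored-data rerun.* For a variable handled by LOCF, removing a Visit 5 value and refilling it replaces a Solo value with a pre-switch one. The gap between runs is then the effect of wrong entries plus the device switch. The same shift formula applies. The documents do not say which variables were unmonitored.
- *Early termination before the switch.* The record is stored as Visit 5. For DTQ change scores, Visit 4 is copied from that same record, so the difference is exactly 0. For the current-status scores, on which SAP 4.2.1.1 bases the Visit 4 to Visit 5 difference, a Visit 4 value filled from Visit 3 gives a difference between two ratings on the randomized device. Neither contains Solo exposure.

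For the last route, let k of 60 subjects in an arm terminate before the switch, and assume no drift on the randomized device. The mean change is multiplied by 1 − k/60. If both arms B and C have k such subjects, the non-Solo share of the overall Visit 5 summary is 2k/180.

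| k per arm | Shrinkage, k/60 | Non-Solo records overall |
|---|---|---|
| 3 | 5% | 6 of 180 (3%) |
| 6 | 10% | 12 of 180 (7%) |
| 11 | 18% | 22 of 180 (12%) |

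Here 11 is the plan's maximum drop-out (0.18 × 60 = 10.8) with all of it before Visit 4, which is the worst case. The counts 3 and 6 are assumptions.

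**3. Primary endpoint route.** It needs an arm B or C subject with no usable Visit 4 DTQ (none, or at most 21 of 30 answers) who starts Solo, later withdraws, and then gives an End of Study DTQ. SAP 3.4.1 ranks that record ahead of Visit 3. Subjects with a usable Visit 4 DTQ, and subjects who withdraw before Visit 4, are not affected.

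Suppose k of 60 MDI subjects score around 110 instead of 90, and let f = k/60. The difference becomes 20(1 − f), the arm B variance 900 + 400f(1 − f), and the arm A variance stays 900. Each affected subject costs 20/60 = 0.33 points. Noncentral-t power at 60 per arm, without covariate adjustment:

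| k | Difference | Power |
|---|---|---|
| 0 | 20.00 | 95.2% |
| 1 | 19.67 | 94.5% |
| 3 | 19.00 | 92.8% |
| 5 | 18.33 | 90.9% |
| 6 | 18.00 | 89.7% |

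The documents give no value of k.

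**The case against.** **Continuing subjects.** A reader might infer that the week-39 Solo DTQ of any B or C subject with an unusable Visit 4 form becomes the week-26 score. The documents do not support that. The End of Study step is tied to withdrawal, and LOCF carries forward, not back. Protocol 11.9 and SAP 2.11 and 6.5 say that all data for the primary analysis exist once every patient has passed Visit 4 or withdrawn. SAP 2.11 repeats the analyses later because the data will then be fully cleaned. This stands, and it leaves only the subject who withdraws after starting Solo. Such cases should be few: questionnaires are completed electronically at the site, and saving one triggers a message to staff: "This will generate a notification to (named) study staff that the questionnaires have been completed/saved" (Protocol 7.13).

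**LOCF of HbA1c and weight.** SAP 3.4.4 speaks of scores, and only where applicable. HbA1c is a measurement, so filling it rests on the referral in SAP 6.13.1 and is not certain. The HbA1c test in SAP 6.8.1.2 uses Visits 2 and 4, so Visit 5 does not enter it. SAP section 6 specifies no by-visit weight analysis, so weight should not be counted as an affected result. All of this stands. What remains is that, if the referral is followed, no rule stops the fill.

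**The rerun.** Any remove-and-impute exercise changes results even when the removed entries were right. That is true. At Visit 5 in arms B and C, however, the replacement comes from a different treatment, which is an additional and avoidable source of difference.

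**Existing safeguards.** The Trt variable (SAP 2.10, 6.2.1) may label an early-termination record by its actual device, but a label does not remove it from by-arm or overall Visit 5 summaries. The per-visit per-protocol set drops subjects who did not complete Visit 4, but the FAS is the primary population (SAP 6.2). Subjects with a telephone Visit 5 count as having completed it. The cover is partial.

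**The remedy.** Analysing only subjects with Solo data at Visit 5 favours those who stayed in the study, and a zero change for the others could be called conservative. The selection is real and must be stated. But a zero from a subject who never used Solo does not estimate a change after the switch.

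**Conclusion.** The gap is real: following SAP 3.4 and 6.13.1 as written can put MDI or OmniPod values into results meant to show Solo use. It mainly concerns secondary, largely descriptive Visit 5 results, including the DTQ change named in Protocol 11.6. Shrinkage of that change is at most about 18%, and only if the maximum drop-out all falls before Visit 4 and there is no drift on the randomized device. The HbA1c shifts rest wholly on assumed shares and changes.

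The primary-endpoint route is a minor point. Under the planning values, power stays above the planned 90% with up to five arm B subjects affected. It would be too strong to say that the primary result is compromised: no count is documented, the text favours the narrow reading, and the bias runs against Solo versus MDI. Severity is minor to should-fix.

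**What to change.** State in SAP 3.4 that no value is carried across the Visit 4 switch in either direction, and add:

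- **Week-26 DTQ.** Use an End of Study DTQ only if it was completed before the end of the parallel phase and, in arms B and C, before first Solo use. Apply the same date cut in arm A. Otherwise use Visit 3, then the stated fallback.
- **Early termination.** Assign records from before the switch to phase 1, outside Visit 5 summaries and Visit 4 to Visit 5 comparisons.
- **Visit 5, arms B and C.** Do not fill from Visit 4. In the 6.13.1 rerun, leave removed Visit 5 values missing.
- **Visit 4 to Visit 5 change, arms B and C.** Report it for subjects with Solo data at Visit 5, and say that it is an observed-case estimate.

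The cost is a few sentences and a date check in the program. Visit 5 has slightly fewer subjects, and a few week-26 scores may fall back to Visit 3. Sample size and hypotheses do not change.

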#### 3.4.2. Incomplete DTQ questionnaires

The handling of questionnaires that are missing completely is described in the previous section. It is however also possible, that questionnaires are only partially completed. Incomplete DTQ questionnaires will be handled according to the questionnaire’s “Scoring Instructions”. As

described above, a score between 1 and 5 is assigned to each possible answer, resulting in a maximum score of 150 if all answers are provided. If at least 22 questions have been answered, the sum score will be divided by the number of answered questions and multiplied by 30 to get a total sum. If 21 or less questions have been answered, the questionnaire will be treated as missing and handled according to the previous section.

### **3.4.3. Handling of empty fields in the diabetes medication forms**

Investigators are only supposed to enter insulin doses if they differ from 0. Consequently, empty fields in the insulin dose fields are considered normal and will simply be imputed with 0 for analysis. Insulin to carbohydrate ratios will be handled similarly. Investigators usually only enter data if they differ from those entered previously. In order to account for this fact, empty values in these forms will be imputed with the value from the previous timepoint. This applies for the variables “Units”, “Grams”, and “mg/dl” respectively “mmol/l” in the diabetes medication forms.

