**Schedule of Assessments**

Procedure \ Visits	Visit 1 Screening	Visit 2 Baseline	Visit 3	Visit 4	Visit 5	Phone Follow up
Time point		day 1	week 13	week 26	week 39	
Time window (+/- days)		0 to +14 days to Visit 1	±14 days	±14 days	±14 days	2-5 days >Visit 5
Informed consent	X 					
Eligibility check (inclusion/exclusion criteria)	X					
Pregnancy test (β-HCG urine) 	X	X 	X 	X 	X 	
HbA 1c in central lab	X 	X	X	X	X	
Demographic data and other Baseline data	X 					
Diabetes & diabetes treatment history	X	X 				
Diabetes medication	X	X 	X 	X 	X 	
Diabetes-associated diseases and treatment	X	X 	X 	X 	X 	
Other diseases and medications	X	X 	X 	X 	X 	
Hypoglycemic events (severe, mild)		X	X	X	X	
Time of absence from work or school		X	X	X	X	
Height & weight		X	X 	X 	X 	
Skin reactions		X	X	X	X	
Subject questionnaires	X		X	X	X	
Randomization	X					
Distribution of devices and other study material		X	X	X		
Pump training		X 		X 		
Carbohydrate Counting Training		X				
Device data download			X	X	X	
A(D)Es/SA(D)Es		X	X	X	X	X 
Malfunctions			X	X	X	
Collect study devices and other study material				X	X	

1 If ongoing A(D)E/SA(D)E at visit 5

2 Written informed consent must be obtained prior to any study related procedure

3 If applicable

CONFIDENTIAL

4 Performed in local lab

5 Year of birth, gender, race; handedness, highest level of education, employment status, family status

6 If any changes

7 Weight only

8 For group A and C

9 if applicable by local law (e.g. in Austria)

10 For group B and C

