### 6.8.2. Diabetes Medication Information

The following diabetes related characteristics will be listed by subject and visit, and tabulated by treatment. For a given visit, always the information from the last change before that visit will be utilized in order to tabulate and list the status at this visit, not the changes.

Additionally, differences between baseline values and V4, between V4 and V5, and between baseline and V5 will be tabulated.

The summary tables for medical history of diabetes will show absolute and relative frequencies for

- Basal insulin used
- Bolus insulin used
- as well as the continuous variable statistics as defined in section 0 for the following variables
- Basal and Bolus doses
- Bolus count

The following information will be listed for each patient and each timepoint specified by the patient

- Insulin sensitivity, glucose target range, carbohydrate factor and the according time range
- Type of basal insulin
- Type of bolus insulin
- Insulin-to-carbohydrate ratio

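### Blank eCRF insulin dose fields become 0 with no check that the dose record was completed, so unrecorded or unmonitored doses can enter the descriptive dose tables as zero insulin

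*SAP*

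**What the plan says.** SAP 3.4.3 covers blanks in the diabetes medication forms. It starts from an entry convention: "Investigators are only supposed to enter insulin doses if they differ from 0". From this it concludes that "empty fields in the insulin dose fields are considered normal and will simply be imputed with 0 for analysis".

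The same section then turns to insulin-to-carbohydrate ratios, which it says are handled in a similar way, and describes a different habit: "Investigators usually only enter data if they differ from those entered previously". For these, "empty values in these forms will be imputed with the value from the previous timepoint". The scope is given as: "This applies for the variables “Units”, “Grams”, and “mg/dl” respectively “mmol/l” in the diabetes medication forms". Units is not defined further.

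The Schedule of Assessments in the protocol, repeated in SAP 3.3, asks for diabetes medication at Visits 2 to 5 only under footnote 6, "If any changes". For the status at each visit, SAP 6.8.2 says that "always the information from the last change before that visit will be utilized", and it lists basal and bolus doses among the variables.

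**The concern.** In this data flow a blank dose field can mean three things: a true zero, a dose unchanged since the last entry, or a dose that nobody recorded. SAP 3.4.3 treats every blank as the first. The convention it cites supports that only where someone filled in the dose record at that visit, and the rule does not make this a condition.

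Total daily and total basal insulin dose are named secondary parameters (Protocol 4.2 and 11.6; SAP 2.1). SAP 6.8.5 reports basal and bolus dose with absolute and relative change from the pre-study value. A total daily dose of zero is implausible in a trial population with type 1 diabetes. A false zero lowers the arm mean, widens the SD and gives that subject a change that did not happen.

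The Covid-19 provision adds a second route. The two-run comparison in SAP 6.13.1 is meant to show how far unmonitored data could influence the results. If removed doses come back as zeros, the comparison for doses shows the effect of the imputation instead.

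**Working it through.** The plan states no dose, blank rate or zero count, so there is no figure of its own to reproduce. The check is a reconciliation of the text, followed by an illustration on assumed inputs.

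**Step 1: follow each kind of blank through the SAP.**

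| Situation | Governing text | Result |
|---|---|---|
| No new entry at the visit because nothing changed | SAP 6.8.2, latest change used | Last recorded dose kept |
| Completed dose record, one field blank because no insulin was given there | SAP 3.4.3 | 0, as intended |
| Dose taken but never recorded | SAP 3.4.3 | 0, false |
| Dose recorded but not monitored, second run | SAP 6.13.1, which sends removed data to section 3.4 | 0 on the literal text, false |

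**Step 2: see whether another rule overrides the zero.** SAP 3.4.4 applies LOCF to other missing scores but excludes the fields covered by 3.4.3, so it does not. For missing device data, including delivered bolus and basal amounts, 3.4.4 uses available information only. The plan therefore avoids inventing values for missing pump-recorded insulin, yet inserts 0 for missing eCRF insulin.

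**Step 3: see where the value is used.** SAP 6.8.2 carries the latest-change rule. SAP 6.8.5, which tabulates eCRF doses by visit, does not repeat it or refer to it. SAP 4.2.3 keeps eCRF and device-upload doses separate, so an upload does not replace a false zero.

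**Step 4: effect on one subject.** With pre-study dose D > 0 and follow-up dose set to 0, relative change = (0 - D)/D = -100%. If the pre-study dose is the one set to 0, the denominator is 0 and relative change is undefined.

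**Step 5: effect on an arm (illustration only).** Let a share f of true non-zero doses be set to 0, with true mean μ and true SD = CV × μ.

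- Mean = (1 - f)μ
- Variance = (1 - f)(SD² + μ²) - ((1 - f)μ)²

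Worked case, with μ scaled to 1, f = 0.10 and CV = 0.3: mean = 0.90; variance = 0.90 × (0.09 + 1) - 0.81 = 0.171; SD = 0.414; SD ratio = 0.414/0.3 = 1.38.

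| Assumed f | Mean falls by | SD multiplied by (CV 0.5 to CV 0.3) |
|---|---|---|
| 2% | 2% | 1.03 to 1.09 |
| 5% | 5% | 1.07 to 1.22 |
| 10% | 10% | 1.12 to 1.38 |
| 20% | 20% | 1.20 to 1.61 |

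Both f and CV are assumptions, and f = 0 is equally compatible with the documents. The calculation sets the subject's whole dose to 0. If only one of several fields is blank, the loss is smaller.

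**The case against.** The zero rule is not arbitrary. It follows from an instruction to sites, and where that instruction was followed a blank in a completed record is a true zero. The rule is also useful at a change of regimen: after a move from injections to a pump, a blank injected-basal field may correctly mean none. This stands, and it is why carrying a whole blank block forward would be the wrong remedy.

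Three stronger readings are tempting and are not supported.

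- **A reader might infer that every unchanged dose becomes 0, because medication is recorded only when it changes.** SAP 6.8.2 prevents this at a visit with no new entry. The sentence about entering only changed data follows the one on carbohydrate ratios and may apply to those fields alone. A form opened for one changed item, with unchanged doses left blank, could still produce zeros. That depends on an eCRF layout the documents do not describe; the form may pre-fill values or require the full regimen.
- **A reader might infer that errors in the MDI arm cannot be checked, since device uploads exist only for pump users.** The protocol provides validation checks and queries (7.13) and source data verification (13.4.1). The SAP adds a Data Review Meeting (section 5), by-subject listings (6.8.2) and a reported minimum (6.3). A zero total could be found. However, 3.4.3 declares blanks normal, so nothing prompts anyone to query them.
- **A reader might infer a definite understatement such as 10%.** The documents give no blank rate.

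The reach is also small. SAP 6.1 allows no testing unless specified, and none is specified for dose.

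**Conclusion.** The point holds in a limited form. SAP 3.4.3 is a stated rule that, followed as written, can turn a dose that was not recorded into zero insulin. Through SAP 6.13.1 it does the same to a real dose that was not monitored. This second route rests on the literal text: 6.13.1 sends removed data to section 3.4, and within that section insulin dose fields fall under 3.4.3.

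The effect is confined to the descriptive secondary eCRF dose tables in SAP 6.8.2 and 6.8.5. Device-upload doses are handled separately, and the primary DTQ analysis is untouched. Per affected subject, a fully zeroed follow-up dose gives a change of -100%. The effect per arm is unknown; the table above gives a scale for assumed rates only and is not an estimate for this trial.

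**What to change.** Amend SAP 3.4.3 and the sections that depend on it:

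1. Impute 0 only for blank fields in a dose record that has at least one non-zero dose entry at that timepoint.
2. Treat a record with all dose fields blank, or a total daily dose of 0, as missing, and query it.
3. If no medication change was reported, use the last recorded doses as in 6.8.2. Do not carry a dose component forward across a change of treatment regimen (Visit 2 for arms A and C, Visit 4 for arms B and C).
4. Treat unmonitored doses removed under 6.13.1 as missing, not as 0.
5. Define Units, so that a programmer can tell whether it is an insulin dose or part of the carbohydrate ratio.
6. Cross-refer 6.8.5 to the rule in 6.8.2.

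Item 1 still relies on the site convention when some doses in a record are filled and others are blank. Only the eCRF layout can settle that case.

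The cost is SAP wording and a few programming checks, with slightly fewer subjects in some dose summaries.
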